| 9.6 | Study Discontinuation..... | 15 |
| 9.7 | Future Use of Stored Specimens..... | 16 |

PROTOCOL SUMMARY

Title:

Evaluating the Feasibility of a Mobile Coaching Intervention to Improve HPV Vaccine Delivery

Summary:

The purpose of this study is to examine the feasibility of using Checkup Coach, a mobile coaching intervention, to improve the way that primary care providers recommend HPV vaccination to adolescent patients and their parents. To conduct this feasibility study, we will deliver the Checkup Coach intervention to Kaiser Permanente Washington primary care providers who routinely recommend HPV vaccine to adolescent patients. We will use a single-arm, pre-post design. Participating primary care providers will attend a 1-hour virtual communication workshop and then use a mobile phone app to receive additional coaching for 12 weeks. Providers will complete surveys at three time points: before the communication workshop, immediately after the workshop, and at 12-week follow-up. Surveys will assess changes in providers' self-reported HPV vaccine recommendation practices and beliefs about HPV vaccine, as well as the acceptability of the intervention. We hypothesize that providers' HPV vaccine communication will improve between baseline and 12-week follow-up.

Objectives:

To evaluate whether the Checkup Coach intervention improves providers' HPV vaccine recommendation quality.

Primary outcome measure: The change in providers' composite score on a 5-item index of self-reported use of HPV vaccine communication practices from baseline to 12-weeks post-intervention.

Sample:

[figure not shown]
Primary care providers who treat 11-12 year old patients in participating Kaiser Permanente Washington pediatric and family medicine practices.

Phase:

Not applicable

| | |
|---|---|
| Study Duration: | June 21, 2021 through January 14, 2022 |
| Participation Duration: | Providers will attend a one-hour communication training workshop and use the Checkup Coach mobile phone app at their discretion for 12 weeks. |
| Description of Intervention: | The Checkup Coach intervention is a 1-hour virtual workshop on HPV vaccine communication, followed by 12 weeks of access to a mobile app that provides additional coaching. |
| Estimated Time to Complete Enrollment: | 4 months |

Schematic of Study Design:

2 INTRODUCTION: BACKGROUND INFORMATION AND SCIENTIFIC RATIONALE

2.1 Background Information

HPV is a highly prevalent sexually transmitted infection associated with over 34,000 cancers in the US each year. The annual cost of screening and treatment for HPV-related diseases totals \$8 billion. Widespread HPV vaccination could prevent the infections that lead to most of these diseases, making the vaccine a powerful tool for cancer prevention.

National recommendations are for the completion of the 2-dose HPV vaccine series at ages 11-12. Timely completion is critical for protecting youth before HPV exposure and may enhance immune response. On-time vaccination, however, is not the norm in the US, with coverage at just 39% for 13-year-olds in 2017. This coverage is far below the Healthy People 2020 goal of 80% for ages 13-15, and suggests that interventions are urgently needed to improve uptake.

The present study seeks to improve healthcare providers' communication about HPV vaccine which is critical to increasing uptake. A provider's recommendation is among the strongest predictors of HPV vaccination. Adolescents who receive a high-quality recommendation versus none have over 9 times higher odds of series initiation. Additionally, interventions that include provider communication training improve HPV vaccination coverage.

Mobile apps are a promising way to extend provider training. Most providers use mobile devices professionally, and apps are an increasingly common vehicle for provider education. Whether app-based coaching could improve providers' HPV vaccine communication is unknown. However, the approach has been successfully piloted in other contexts (e.g., critical care), suggesting promise.

2.2 Rationale

Our study seeks to evaluate the feasibility of Checkup Coach, a quality improvement (QI) coaching intervention, including a mobile app, that we have developed to deliver HPV vaccine communication training. At the provider level, Checkup Coach is designed to improve HPV vaccine communication via ongoing assessment and tailored feedback.

At the clinic level, the app will provide quality improvement tools, including graphs of clinics' and providers' HPV vaccine coverage (i.e., % of patients vaccinated), for tracking shared goals for improvement. We will conduct this study to evaluate the feasibility of using the QI coaching intervention to improve HPV vaccine communication in primary care settings. If successful, this study will inform the future development of a randomized controlled trial to examine the impact of the Checkup Coach intervention on HPV vaccine uptake.

2.3 Potential Risks and Benefits

2.3.1 Potential Risks

Potential short-term risks associated with participation include healthcare providers' loss of time and slight risk of embarrassment or discomfort in answering questions about their HPV vaccine recommendation practices. However, because the communication workshop is brief (<1 hour) and app use is discretionary, we expect loss of time to be minimal. Additionally, providers will have the option to refuse to answer any survey questions and can decline to use the mobile app. All answers to survey questions and data entered into the app will be kept confidential. Thus, the risk of embarrassment is anticipated to be very slight.

We do not anticipate immediate or long-range risks associated with participation.

2.3.2 Known Potential Benefits

By participating in this study there is a potential to increase provider knowledge and confidence for recommending HPV vaccination as a routine preventive service for adolescents. This study will also help inform a future larger randomized trial of the Checkup Coach intervention. The goal of that trial would be to develop a quality improvement tool that will help increase HPV vaccination coverage which could reduce the future incidence of HPV-related cancers.

3 OBJECTIVES

3.1 Study Objectives

The purpose of this study is to examine the feasibility of using Checkup Coach, a QI coaching intervention, to improve primary care providers' use of evidence-based communication practices to support routine HPV vaccination.

3.2 Study Outcome Measures

Outcome measures will be changes in providers' HPV vaccine recommendation practices and the feasibility of the Checkup Coach quality improvement intervention. Data will come from provider surveys at three time points and mobile app usage data.

3.2.1 Primary Outcome Measures

For each participating provider, we will assess the change in composite score on a 5-item index of self-reported HPV vaccine recommendation quality from baseline to 12-week post-intervention. Scores range from 5-25 (5 indicating the lowest quality score to 25 indicating the highest quality score).

3.2.2 Other Measures

We will assess the feasibility of the Checkup Coach intervention by evaluating:

- Use of the Checkup Coach mobile coaching app (measured as % of providers who use the Checkup Coach mobile app, assessed using app analytics; and measured as the mean number of times that app users access the app, assessed using app analytics).
- Intervention acceptability (measured as mean ratings for intervention convenience, organization, helpfulness, and whether participants would recommend it to a colleague, assessed using 5-point survey items).

4 STUDY DESIGN

This study will evaluate the Checkup Coach intervention using a single-arm, pre-post design with approximately 20 primary care providers at Kaiser Permanente Washington (KPWA). The intervention has two main components. In the first part of the intervention, participants attend a communication training workshop via a virtual conferencing platform. The workshop will be conducted by study staff and the KPWA Director of Preventive Care. The brief (<1 hour) workshop reviews evidence on HPV vaccination, models guideline-consistent recommendation practices, trains providers to address common parent concerns, and facilitates discussion of shared goals for improving. Workshop content is evidence-based and reflects communication practices supported by research evidence and recommended by the Centers for Disease Control and Prevention. At the end of the workshop, providers are asked to download and practice using the Checkup Coach mobile app.

In the second part of the intervention, which starts after the communication training, providers are invited to use the Checkup Coach mobile app for 12 weeks. The app is a QI tool designed to provide tips and tools for improving HPV vaccine communication. App functions include: (a) provider self-assessment of HPV vaccine recommendation practices; (b) feedback on their HPV recommendation quality in the form of a “recommendation goal score”; (c) research-tested messages for addressing parent concerns that are tailored to in-app self-assessments; and (d) a dashboard with graphs of provider- and clinic-level HPV vaccination coverage (i.e. % of 11-12 year old adolescents vaccinated).

5 STUDY ENROLLMENT AND WITHDRAWAL

5.1 Subject Inclusion Criteria

In order to be eligible to participate in this study, a provider must:

- Be a primary care provider in an invited KPWA pediatric or family medicine clinics in the Puget Sound/Spokane area
- Regularly treat adolescent patients, ages 11-12

5.2 Subject Exclusion Criteria

Providers not eligible to participate:

- Provide care in a clinic not invited to participate in the study
- Do not regularly treat adolescent patients, ages 11-12

5.3 Strategies for Recruitment and Retention

The KPWA Medical Director for Preventive Care will identify KPWA primary care clinics in the Puget Sound/Spokane area that administer HPV vaccine to adolescent patients, ages 11-12. He will invite clinics to participate in the study by contacting each site's clinical director. Once clinical directors agree to have their clinics participate, study staff will invite all primary care providers who regularly treat 11-12 year old patients in each clinic to participate.

5.4 Treatment Assignment Procedures

5.4.1 Randomization Procedures

None.

5.4.2 Masking Procedures

None.

5.4.3 Reasons for Withdrawal

Participants who request to withdraw will be given the option to discontinue participation in the intervention but continue participation in follow-up data collection activities.

Participants who refuse this offer and request to completely withdraw from the study will no longer be contacted. There will be no investigator-initiated withdrawal.

5.4.4 Handling of Withdrawals

See above.

5.4.5 Termination of Study

Given the low-risk nature of this study, we do not anticipate grounds for premature termination.

6 STUDY INTERVENTION

6.1 Study Intervention Description

The Checkup Coach intervention offers two main components to primary care providers who care for adolescent patients: a webinar communication workshop and use of the Checkup Coach mobile app.

1. Communication Workshop. The Checkup Coach intervention begins with a brief (<1 hour), communication training workshop. Using a script and slides, the KPWA Director for Preventive Care and the study PI will meet with participating providers over a web-based meeting platform to: review evidence on HPV vaccination; model high-quality, guideline-consistent recommendations; train providers to address parent concerns; and facilitate discussion of shared goals for improving.

At the end of the training, providers will be asked to download and begin using the Checkup Coach app. Downloading and using the app will be voluntary, and providers can consent to participate in the webinar training but decline all other study activities.

2. Checkup Coach app. Providers will be invited to use the Checkup coach mobile app at their discretion for the 12 week study period. If they have push notifications enabled, providers will be sent push notifications reminding them to use the app up to six times over the 12 week period. Providers will complete the in-app self-assessments and receive tailored feedback every time they use the app.

A detailed description of the Checkup Coach self-assessment and tailored feedback is as follows:

- Self-assessment of recommendation quality. Providers complete a very brief in-app self-assessment to determine how often in the last week they used 5 practices effective for recommending HPV vaccine according to national guidelines. Guidelines include delivering recommendations on time (i.e., ages 11-12), consistently to all eligible patients, and offering same-day vaccination services when possible. The app adds 5-point

response options to give an overall score and to identify areas for improvement.

- Recommendation Goal Score. The app displays a bar chart of providers' overall self-assessed recommendation quality score in reference to the goal of 5 (i.e., "almost always" using all 5 practices).
- Dashboard. The app presents line graphs of aggregate HPV vaccination coverage (i.e., % of patients vaccinated) over the study period for both the individual provider and their clinic.
- Tips for addressing HPV vaccine communication challenges. Providers complete an in-app 5-item self-assessment to identify parent concerns they "often" or "almost always" find difficult to ease. The app pulls from a library of 15 messages to suggest a research-tested response tailored to each concern (called "Tips for Talking to Parents" in the app). Those who indicate no concern receive randomly selected messages with encouragement to keep up their good work.

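### Does a goal of 5 contradict an in-app score described as adding five 5-point items?

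*Combined protocol and SAP*

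**What the plan says.** Section 6.1 describes two linked functions of the app.

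- **Self-assessment.** Providers report "how often in the last week they used 5 practices effective for recommending HPV vaccine according to national guidelines". The scoring sentence is split by a line break in the text: "The app adds 5-point", continuing "response options to give an overall score and to identify areas for improvement".
- **Recommendation goal score.** A bar chart shows the provider's "overall self-assessed recommendation quality score in reference to the goal of 5 (i.e., 'almost always' using all 5 practices").

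Section 4 lists this display among four app functions, as "feedback on their HPV recommendation quality in the form of a" goal score.

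Section 3.2.1 defines a separate survey measure as the primary outcome: the "change in composite score on a 5-item index of self-reported HPV vaccine recommendation quality from baseline to 12-week post-intervention". Its range is stated: "Scores range from 5-25 (5 indicating the lowest quality score to 25 indicating the highest quality score").

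**The concern.** If the app sums five graded items, using every practice *almost always* should sit at the top of the summed scale. Five is not the top of such a scale under the usual codings. On the 5-25 scale that Section 3.2.1 gives for a similarly described five-item index, 5 is the worst possible score. A reader who sets the two sections side by side finds the same number marking the lowest quality in one and the goal in the other.

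The stake would be the feedback. A target of 5 on a 5-25 scale would be met by every provider whatever they answered, and the chart would give no reason to improve. A team copying the intervention from Section 6.1 alone could not tell how the score is formed.

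**Working it through.** **Inputs.** Five practices and 5-point response options (Section 6.1); a goal of 5, defined as *almost always* on all five (Section 6.1); a survey index range of 5-25 (Section 3.2.1). Two inputs are assumptions: the numeric coding of the app's options, which is not stated, and that *almost always* is the top option.

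**Step 1: the survey index.** With k = 5 items coded from a to b, the sum runs from k × a to k × b. With 1-5 coding this is 5 × 1 = 5 to 5 × 5 = 25. The range in Section 3.2.1 is reproduced, so the primary outcome is consistent with a plain sum.

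**Step 2: the app score for top performance on all five practices.**

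| Rule | Coding | Calculation | Score | Equals the goal of 5? |
|---|---|---|---|---|
| Sum | 1-5 | 5 × 5 | 25 | no |
| Sum | 0-4 | 5 × 4 | 20 | no |
| Sum, *almost always* as fourth option | 1-5 | 5 × 4 | 20 | no |
| Mean | 1-5 | 25 / 5 | 5 | yes |
| Mean | 0-4 | 20 / 5 | 4 | no |
| Count of practices at the top option | – | 5 | 5 | yes |
| Sum | 0 to 1 in steps of 0.25 | 5 × 1 | 5 | yes |

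Read literally on a 5-25 sum, a goal of 5 lies at (5 − 5) / (25 − 5) = 0 of the range, the floor.

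The mismatch is therefore real for an ordinary sum, but it is not forced. Five response options fix the number of categories, not the values attached to them. The last row is an unusual coding, yet it satisfies both statements. The scoring sentence can also be read, less naturally, as saying that the app supplies graded options from which a score and weak areas are derived; on that reading no summing rule is stated at all.

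**Step 3: where the in-app score is used.**

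- Section 3.2.1: the primary outcome is the survey index, not the app score.
- Section 3.2.2: app data supply the percentage of providers using the app and the mean number of accesses. Acceptability comes from survey items.
- Section 8.4: the Wilcoxon signed-rank tests use the survey index, survey items and a knowledge index.

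No planned estimate or test takes the in-app score as input. Whichever row of the table describes the app, the planned analyses are the same.

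**The case for a change.** The strongest case for a change is that the feedback is part of the intervention. Section 6.1 has providers receive tailored feedback each time they use the app, Section 2.2 names such feedback as a means of improving communication, and the study is meant to prepare a randomised trial. The rule should then be reproducible. The candidate rules are not interchangeable: a provider answering 4 on all five items has a mean of 20 / 5 = 4.0 but a count of 0 practices at the top option. One sentence would settle it at no cost.

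Part of this stands. The section does not let a reader choose between a mean and a count, and a fuller description would be tidier. But Section 2.2 says the team has already developed the intervention, including the app. Section 6.1 summarises an existing tool, and nothing suggests that the app was built from it. The sentence that gives the 5 also says in words what it represents, so the top of the scale is plainly meant. Nothing in the documents indicates that providers were shown a target at the floor. The pre-post comparison also evaluates the app as delivered, and rewording Section 6.1 would not alter what was delivered.

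**Conclusion.** No change to the plan is called for. Section 6.1 is loosely worded: under 1-5 or 0-4 coding a sum would put the described goal at 25 or 20, while the stated 5 fits a mean, a count, or items scaled 0 to 1. The intended meaning is clear from the sentence itself. The consequence for the primary outcome, the feasibility measures and the Wilcoxon tests is zero, because none of them uses the score.

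This rests on *almost always* being the top response option, and on the app's chart showing the top of its scale as the goal. The documents do not show the display, so the second point cannot be confirmed from them. If it were false, the fault would lie in the app and not in the statistical plan. The 5-25 range in Section 3.2.1 belongs to a separate survey instrument and cannot by itself prove the app's figure wrong.

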6.2 Dosage, Preparation and Administration of Study Intervention

Each primary care provider will attend one communication workshop which will last less than one hour. They will then be able to use the mobile app, at their discretion, for up to 12 weeks.

6.3 Modification of Study Intervention for a Subject

Not applicable.

6.4 Accountability Procedures for the Study Intervention

Not applicable.

6.5 Assessment of Subject Compliance with Study Intervention

Not applicable.

6.6 Concomitant Medications/Treatments

Not applicable.

7 STUDY SCHEDULE

7.1 Screening

Screening of eligible clinics and providers will be conducted by the KPWA Director of Preventive Care, using data from KPWA's internal records.

7.2 Enrollment/Baseline

Enrollment and pre-workshop data collection will occur simultaneously from July – September 2021. Communication workshops and post-workshop data collection will occur in the same period, from July – September 2021.

7.3 Follow-up

Mobile app use and data collection through the app will occur from July – December 2021. Twelve-week follow-up data collection will occur from October 2021 – January 2022.

7.4 Final Study Visit

Not applicable.

7.5 Early Termination Visit

Not applicable.

7.6 Unscheduled Visit

Not applicable.

8 STATISTICAL CONSIDERATIONS

8.1 Study Hypotheses

The Checkup Coach intervention will increase providers' HPV vaccine recommendation quality score.

8.2 Sample Size Considerations

We will test our hypothesis that Checkup Coach will increase providers' overall recommendation quality over the 12-week study period with approximately 20 providers. We acknowledge that our trial is underpowered to detect small differences or control for multiple testing. The purpose of a feasibility study is to estimate effect sizes for powering a large-scale RCT. By piloting our intervention in 5 or more different clinics, our study is designed to provide the data needed to lay this groundwork.

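### The objective, the hypothesis and section 8.2 treat an uncontrolled pre-post change in a self-reported score as the intervention's effect and as an effect size for a later RCT; a single-arm design can supply neither.

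*Combined protocol and SAP*

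**What the plan says.** Three statements in the combined protocol and SAP assign the change in score to the intervention, or rely on that assignment:

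- Protocol Summary, Objectives: "To evaluate whether the Checkup Coach intervention improves providers' HPV vaccine recommendation quality".
- Section 8.1: "The Checkup Coach intervention will increase providers' HPV vaccine recommendation quality score".
- Section 8.2 says this hypothesis will be tested in about 20 providers, then states: "The purpose of a feasibility study is to estimate effect sizes for powering a large-scale RCT".

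The design is described openly. The Summary says "We will use a single-arm, pre-post design", and sections 5.4.1 and 5.4.2 record that there is no randomization and no masking. The primary outcome (3.2.1) is the change in a five-item self-report score, range 5 to 25. The only primary analysis (8.4) is a within-provider Wilcoxon signed-rank test of baseline against 12 weeks. Of the three surveys, only the pre-workshop one precedes the intervention.

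Milder wording also appears. Section 3.1 reads: "The purpose of this study is to examine the feasibility of using Checkup Coach, a QI coaching intervention, to improve primary care providers' use". Section 8.4 speaks of assessing change, and one Summary sentence predicts only that communication will be better at 12 weeks than at baseline. Section 2.2 names HPV vaccine uptake as what the later RCT will examine. The limitation admitted in 8.2 is low power for small effects and no control of multiplicity.

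**The concern.** An RCT's effect is a difference between arms. A change within one arm is that difference plus whatever untrained providers would have shown over the same 12 weeks: change with calendar time, the effect of answering the same survey again, regression to the mean, and a pull towards the answer the study team is known to want. The last of these deserves attention here, because the outcome is self-reported by unmasked providers who have just been taught which practices are desirable.

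Two things are at stake. First, section 8.1 as worded would count a significant signed-rank test as support for a causal hypothesis, whatever produced the change. Second, 8.2 presents the result as an effect size for powering an RCT, and nothing in the plan warns that the number is not of that kind. The limitation it does admit is about precision. Enrolling more providers would help with that and would do nothing for attribution.

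**Working it through.** **What the plan gives.** About 20 providers (8.2); one arm (Summary, section 4); baseline and 12-week scores on a 5 to 25 index (3.2.1); a signed-rank test (8.4). No alpha, power, expected change, SD or correlation is stated, so there is no sample-size figure to reproduce.

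**Step 1: what the contrast estimates.** Let τ be the intervention effect and b the mean change the same providers would have shown without it. Then

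expected pre-post change = τ + b.

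Every provider contributes one pre-intervention score and one 12-week score, both under the intervention path, so nothing in the data separates τ from b. The survey taken straight after the workshop does not help, because it already follows part of the intervention.

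**Step 2: what this does to the planned test.** Assumptions: normal change scores, n = 20, two-sided 5%, τ = 0, and b in units of the SD of the change. Share of 10,000 simulated studies with a significant improvement:

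| assumed b | significant improvement |
|---|---|
| 0 | about 2% |
| 0.2 SD | about 13% |
| 0.3 SD | about 24% |
| 0.5 SD | about 55% |

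With no intervention effect at all, a modest background change can produce a result that 8.1 would read as confirmation. The values of b are assumptions; the documents give none.

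**Step 3: imprecision is a separate problem.** The 95% half-width for a mean change at n = 20 is t(0.975, 19)/√20 = 2.093/4.472 = 0.47 SD of the change. That shrinks as n grows; b does not.

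**Step 4: consequence if the change were used to size a trial.** Write f = b/(τ + b), the share of the observed change that controls would also show. Required size is proportional to 1/(difference)², so

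n needed / n planned = (τ + b)²/τ² = 1/(1−f)².

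For a trial planned at 80% power, two-sided 5%, the normal approximation gives power = Φ(2.80 × (1−f) − 1.96).

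| f | size multiplier | power actually achieved |
|---|---|---|
| 0 | 1/1² = 1 | Φ(0.84) = 80% |
| 25% | 1/0.75² = 1.78 | Φ(0.14) = 56% |
| 50% | 1/0.5² = 4 | Φ(−0.56) = 29% |

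This holds only on a matched scale: the pilot change and the RCT difference must be divided by the same SD. If the pilot uses the SD of the change and the RCT compares follow-up scores, the standardized value must first be multiplied by √(2(1−r)), where r is the baseline-to-follow-up correlation. It also ignores any clustering by clinic.

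**Step 5: the endpoint.** Set 8.2 beside 2.2. The quantity estimated here is in points on a self-report index. The RCT that 2.2 describes concerns vaccine uptake. The documents give no conversion from one to the other, so even with b = 0 the pilot change would not directly size that trial.

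**The case against.** The strongest reply is that this is a feasibility study and mostly says so. The single arm and lack of masking are plain, section 3.1 states a feasibility purpose, 3.2.2 lists app use and acceptability, and 2.2 leaves the question of impact to the RCT. All of that stands. One arm is adequate for those feasibility measures, and no control arm is being asked for. But the causal objective and hypothesis conflict with that framing, and the feasibility sections do not withdraw them.

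Four stronger readings are tempting and not supported:

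- A reader might infer that the result is confounded by season. Baselines fall in July to September (7.2) and follow-ups in October to January (7.3), but nothing in the documents shows that self-reported communication varies by season. Twelve weeks from 1 July and 30 September end on 23 September and 23 December, so most pairs run from summer into autumn. Later calendar time goes with the post measurement in any single-arm study.
- A reader might infer that the change will be entered in the RCT calculation as the between-arm difference. No section says so, and the uptake endpoint in 2.2 makes direct entry impossible. The defect is that 8.2 states a purpose the study cannot serve.
- A reader might infer that the app trains providers on the outcome items themselves. Section 6.1 describes an in-app rating of five practices scored against a goal, so overlap is plausible. The five survey items are not listed and app use is voluntary, so it is not established.
- A reader might infer that the change must be too favourable. Background change could go either way, and eligibility does not select on baseline score, so regression to the mean may be small. The point is that b is unknown, not that it is known to be positive.

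**Conclusion.** The concern holds as a mismatch between what the plan claims and what its design can deliver. The Summary objective and 8.1 attribute the change to the intervention, and 8.2 gives effect-size estimation for an RCT as the purpose. The planned contrast estimates the intervention effect plus background change, on an endpoint different from the RCT's, and the admitted limitation does not cover either gap.

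No numerical size can be put on the error from the documents. The multipliers of 1.78 and 4 are illustrations for assumed f of 25% and 50% on a matched scale; the documents give no f and this design cannot supply one. The conclusion does not depend on those values. It rests only on the absence of any comparison without the intervention. The feasibility measures in 3.2.2 are unaffected.

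**What to change.** 1. Reword the Summary objective and section 8.1 as estimating the within-provider change in self-reported recommendation quality from baseline to 12 weeks. Add that the change will not be attributed to the intervention because there is no control group.
2. In section 8.2, replace the effect-size purpose. State that the study supplies feasibility, retention, app-use and variability inputs, that the observed pre-post change will not be used as the RCT's between-arm difference, and that this difference will be justified separately on the uptake endpoint.

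Both changes bring these sentences into line with wording already in section 3.1, section 8.4 and the Summary. No data collection, visit or analysis changes. The cost is a less favourable stated claim, and the RCT team must justify its target difference from another source.
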